However, by the mid-2000's, a growing number of adverse event reports had been submitted to the MAUDE FDA database related to trans-vaginal synthetic mesh products used for these indications. During 2005-2010, MAUDE received 1371 reports of injury, death, and malfunction of mesh for SUI treatment, related to mesh erosion, pain, infection, recurrence of urinary symptoms, and organ perforation, along with a 5-fold increase in MAUDE reporting rates in 2008-2010 compared to 2005-2007. While these numbers increased scrutiny surrounding these devices, a lack of denominator data and a reliance on voluntary reporting that is sensitive to FDA and press scrutiny limit the interpretability of these findings.

Risk assessments around synthetic surgical mesh for SUI remains uncertain for some outcomes extending beyond one year²⁵. [name] and colleagues evaluated a New York State prospective registry (SPARC) that included all surgeries and evaluated 41,604 women undergoing mesh implantation for pelvic organ prolapse or stress urinary incontinence. Among the 22,252 women undergoing surgery for SUI, 1.6% of them had mesh erosions that required intervention²². In one UK study, overall re-operation rates were only 3.2% among mid-urethral sling procedures for SUI after a median 2.8 years of follow-up²⁶. In a private US claims database, the cumulative re-operation rate was 14.5% after a median 9 years of follow-up²⁷, with sling revision/removal at 3.7%²⁸. Other small studies in non-US populations have shown low rates of long-term complications (1-3%)²⁹. A recent UK study among 95,057 women and a median follow-up time of 5.5 years found that risk of re-operation was 2.6% at 1 year, 5.5% at 5 years, and 6.9% at 9 years³⁰. More specifically, mesh removal rates were 3.3% at 9 years in this population. Another UK study among 92,246 patients with first time mesh implantations for SUI found a 5-year complication rate of 9.8%³¹. A Canadian study of 59,887 women found ~3.5% may require mesh removal or revision within 10 years of initial surgery³².

There have also been some systematic reviews and meta-analyses done attempting to further understand the complications in this population. In 2015, a systematic review of studies with a follow-up of 36 months for TOMUS and 60 months for RPMUS were searched and studies comparing the two were

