8.1 DATA COLLECTION AND MANAGEMENT

As shown in Figure 1, we will access the data in each institution through the PCORNet or OMOP common data models, which are a normalized sub-set of EHR data that allows standardization of data representation and analytic processes. All sites but Lahey have PCORNet instituted through participation in PCORNet, and Lahey has OMOP. There is a publicly available transform from OMOP to PCORNet that will be utilized to harmonize Lahey to PCORNet. The data available across all sites is limited to patient demographics, inpatient and outpatient administrative condition and procedure codes (ICD-9/10, ICD-9/10 Procedure, CPT, HCPCS, SNOMED-CT), medication orders and/or fills/administrations, laboratory test results, vital signs, and date of death. We prefer prescribing if both are available. The PCORNet common data models in each site except Lahey have undergone extensive data quality assessment through data characterization queries where gaps and systematic miscoding have been reported and addressed over the course of the PCORNet CDRN network lifespan.

[figure not shown]

Figure 1: Summary of data collection and data flow process at each site for the variable transformation and distributed regression portions of the project.

Each of the participating sites will supplement their existing CDM-based structured data with free text peri-operative documents for those patient cases that has mesh implantation for stress urinary incontinence, as defined and identified elsewhere. As procedural codes are date specific, all documents +/- 2 days of the administrative code date will be extracted. Notes will then be further filtered to include only 2 notes for each surgical case, the pre-operative planning note (Surgeon, Anesthesia, or Nursing) and the operative note. Sample size estimates are based on a number of referent publications.^{50,51} Each site will randomize their patient population and initially select 600 patient documents among 300 patients (2 documents per patient, the primary operative note and a random note from the other notes included) for each surgery. Each site will determine what the surgical approach is at the document level (document assignment) and patient level (merging the 2 document assignments). Vanderbilt will annotate an additional 100 patients to serve as the primary training data set (100 training, 100 internal validation).

Version 2.0 [15 July 2020]

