		 Mesh exposure and erosion (ICD9/10 629.31, 629.32/T83.711, T83.721) Urinary Retention (CPT Code 53500, ICD 9/10 788.20, 788.21/R33.0, R33.8-R33.9) Urgency of urination (ICD9/10 788.63/R39.15) Urge incontinence (ICD9/10 788.31/N39.41) Bowel injury (ICD9/10 569.83/S36) Bladder/urethral injury (ICD9/10 596.6,867.0/S37) Infection (ICD9/10 686.9,998.5,999.3,998.51,998.59/T81) Retropubic hematoma (ICD 9/10 568.81,,568.81,459.0/K66.1) Retopubic hematoma (ICD 9/10 568.81,,568.81,459.0/K66.1) Retopubic hematoma (ICD 9/10 568.81,568.81,459.0/K66.1) Bulking Injection CPT 51715, ICD 9/10 59.72/ PCS 3E0K3GC Laparoscopic Retropubic Urethropexy CPT 51990, 51992, 51999 Abdominal Retropubic Urethropexy CPT 51840,51841 Needle Bladder Neck Suspension CPT 51845 Kelly plication CPT 57220 Cystourethroplasty CPT 51800 Subtypes: Stress incontinence, female/mixed incontinence (ICD9/10 625.6,788.33/N39.46) Stress incontinence (female) (male)(ICD10 CM N39.3) 		
Outcome	Mesh Removal	 General, CPT 57287-Removal or revision of sling for stress incontinence (fascia or synthetic) ***some erosions managed surgically may have been coded by a different CPT (i.e. 57295 revise vaginal graft via vaginal approach) and not CPT 57287, which indicates a sling revision/removal. 	Yes	Possible Options: (a surgery for any kind of mid-urethral sling, urethral bulking agent, black neck pubovaginal sling (autologous or allograft), or revision for mesh exposure). Represented as a Date, allows time-to-event analysis.
Outcome	Post-Procedural Pain	?, mix of vital sign (pain score >3 of 10 on vital sign data) and likely free text. Also, diagnosis codes related to abd/pelvic pain (if prior pain free).	Some portion	Would have to exclude prior chronic pain or detect specific mention of new pain (free text). Could analyze group with no pre-surgical pain,

Protocol 1				[15 July 2020]
				otherwise probably beyond scope. Date/Time of first post- op occurrence.

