	45114, 45119, 45120, 45121, 45123, 44204,	
	44205, 44206, 442Ø7, 442Ø8, 4421Ø, 44211,	
	44212, 44213, 44238, 45395, 45397/45.8, 45.81,	
	45.82, 45.83/0DTE4ZZ, 0DTE0ZZ, 0DTE7ZZ,	
	ODTE8ZZ	
	Lysis of abdominal adhesions: 44108, 44005,	
	58660, 58740, 53500/ 54.5, 54.51,	
	54.59/0DN84ZZ, 0DNE4ZZ, 0DNJ4ZZ, 0DNU4ZZ,	
	ODNV4ZZ, ODNW4ZZ, OFN04ZZ, OFN44ZZ,	
	OFN48ZZ OFN54ZZ, OFN64ZZ, OFN74ZZ, OFN84ZZ,	
	OFN94ZZ, OFNG8ZZ	
	Oophorectomy- 58661, 49321-51,	
	58940/V45.77/ Z90.722, Z90.721	
	555 10, 145.11, 250.122, 250.121	
	Cystocele and rectocele repair- 57260-51, 57282,	
	57267, 57270, 61809, 57240/70.50/ 0JQC0ZZ,	
	0JQC3ZZ	

Protocol 1			•	[15 July 2020]
		Gastrectomy- 43631, 43632, 43633,		
		43634/V45.75/Z90.3		
		Hystorestemy ⁵⁴ abdominal and vaginal		
		Hysterectomy ⁵⁴ , abdominal and vaginal C section		
		Appendectomy		
		Hernia repair		
		Cholecystectomy		
		Colectomy or colorectal resection		
		Excision, lysis peritoneal adhesions		
		Oophorectomy, unilateral and bilateral		
		Repair of cystocele and rectocele, obliteration of		
		vaginal vault		
		Gastrectomy		
		Other		
Outcome	Surgical Site Infection	Admin Codes & Free Text	Partially	Capture as date/time
		Pelvic, perineal abscess, or infection due to		Lahey Question:
		internal prosthetic device, implant and graft		Can antibiotic use in
		Infection due to implant:		within X days be a proxy
		996.69/T85.79XA		for SSI?
		Pelvic abscess ICD9/10:567.22/K65.1		
		614.3/N73.0		
		614.9 or 616.9/N73.9		
		614.4/N73.1		
		614.5/N73.5, N73.3		
		014.5/10/5.5/10/5.5		
		Perineal abscess ICD9/10:		
Outcome	Organ Mesh	682.2/L02.215 Admin Codes & Free Text (Possibly)	Vec	Direct surgical
Outcome	Organ Mesh	Admin Codes & Free Text (Possibly)	Yes	Direct surgical
Outcome	Perforation	Admin Codes & Free Text (Possibly) • Erosion of other implanted mesh to	Yes	complication, capture as
Outcome	Perforation (vagina, urinary	Admin Codes & Free Text (Possibly) • Erosion of other implanted mesh to organ or tissue ICD10CM-T83.712	Yes	_
Outcome	Perforation	Admin Codes & Free Text (Possibly) Erosion of other implanted mesh to organ or tissue ICD10CM-T83.712 Erosion of implanted urethral mesh to 	Yes	complication, capture as
Outcome	Perforation (vagina, urinary	 Admin Codes & Free Text (Possibly) Erosion of other implanted mesh to organ or tissue ICD10CM-T83.712 Erosion of implanted urethral mesh to surrounding organ or tissue, initial 	Yes	complication, capture as

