Outcome	Perforation (vagina, urinary	 Admin Codes & Free Text (Possibly) Erosion of other implanted mesh to organ or tissue ICD10CM-T83.712 Erosion of implanted urethral mesh to surrounding organ or tissue, initial encounter-T83.712A Erosion of implanted urethral mesh to surrounding organ or tissue subsequent encounter-T83.712D Erosion of implanted urethral mesh to surrounding organ or tissue subsequent encounter-T83.712D Erosion of implanted urethral mesh to surrounding organ or tissue, sequela- 	Yes	complication, capture as
Outcome	Perforation (vagina, urinary	 Admin Codes & Free Text (Possibly) Erosion of other implanted mesh to organ or tissue ICD10CM-T83.712 Erosion of implanted urethral mesh to surrounding organ or tissue, initial encounter-T83.712A Erosion of implanted urethral mesh to surrounding organ or tissue subsequent encounter-T83.712D Erosion of implanted urethral mesh to surrounding organ or tissue, subsequent encounter-T83.712D Erosion of implanted urethral mesh to surrounding organ or tissue, sequela-T83.712S 	Yes	complication, capture as
Outcome	Perforation (vagina, urinary	 Admin Codes & Free Text (Possibly) Erosion of other implanted mesh to organ or tissue ICD10CM-T83.712 Erosion of implanted urethral mesh to surrounding organ or tissue, initial encounter-T83.712A Erosion of implanted urethral mesh to surrounding organ or tissue subsequent encounter-T83.712D Erosion of implanted urethral mesh to surrounding organ or tissue subsequent encounter-T83.712D Erosion of implanted urethral mesh to surrounding organ or tissue, sequela-T83.712S Exposure of implanted urethral mesh into urethra ICD10-T83.722 	Yes	complication, capture as
Outcome	Perforation (vagina, urinary	 Admin Codes & Free Text (Possibly) Erosion of other implanted mesh to organ or tissue ICD10CM-T83.712 Erosion of implanted urethral mesh to surrounding organ or tissue, initial encounter-T83.712A Erosion of implanted urethral mesh to surrounding organ or tissue subsequent encounter-T83.712D Erosion of implanted urethral mesh to surrounding organ or tissue subsequent encounter-T83.712D Erosion of implanted urethral mesh to surrounding organ or tissue, sequela-T83.712S Exposure of implanted urethral mesh into urethra ICD10-T83.722 Exposure of implanted urethral mesh 	Yes	complication, capture as

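### The Organ Mesh Perforation row lists only erosion and exposure codes, the Mesh Erosion outcome omits those codes, and organ-injury codes count only under re-operation

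*Protocol*

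**What the plan says.** All of the relevant definitions are in the Data Collection table of Section 13.

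- **Organ Mesh Perforation (vagina, urinary tract)** is classed as an outcome. Its source is given as "Admin Codes & Free Text (Possibly" and its note begins "Direct surgical", continuing to call it a complication to be captured with a date. The codes are T83.712 with suffixes A, D and S, opening with "Erosion of other implanted mesh to organ or tissue ICD10CM-T83.712", and T83.722 with the same suffixes, opening with "Exposure of implanted urethral mesh into urethra ICD10-T83.722".
- **Mesh Erosion** is a separate outcome row. Among codes whose labels say erosion or exposure, it names those for vaginal mesh (629.31/T83.711 and 629.32/T83.721S). It also has a set of broader device-complication codes. T83.712 and T83.722 are not in it.
- **Re-Operation** holds the organ-injury codes, as subtypes of re-operation for mesh revision or removal: "Bladder/urethral injury (ICD9/10 596.6,867.0/S37" and "Bowel injury (ICD9/10 569.83/S36". Its own erosion and exposure subtype also uses only T83.711 and T83.721.

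The synopsis and Section 3 list mesh erosion among the outcomes whose rates are to be assessed. Organ perforation is in neither list, and it is not a primary outcome in Section 7.

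**The concern.** The row's title and note suggest damage done by the operation, but its codes describe mesh that has eroded or become exposed. The background in Section 1.1 names the two separately when it describes adverse-event reports "related to mesh erosion, pain, infection, recurrence of urinary symptoms, and organ perforation", and the appendix gives erosion a row of its own.

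Two reported rates are at stake. The perforation rate would be built from erosion and exposure codes. The erosion rate, in a study of mid-urethral slings, would lack the codes that the appendix itself labels as urethral mesh. An injury at the index operation would enter the results through the listed injury codes only if a re-operation followed.

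**Working it through.** The plan states no figure for this outcome, so the check is a count of codes and a comparison of rows.

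**Step 1: count the entries in the perforation row.**

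| Code | Entries | Label |
|---|---|---|
| T83.712, T83.712A, T83.712D, T83.712S | 4 | erosion |
| T83.722, T83.722A, T83.722D, T83.722S | 4 | exposure |

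Total: 4 + 4 = 8. Labelled erosion or exposure: 8 of 8. Labelled injury or perforation: 0 of 8. Seven labels specify urethral mesh. The first refers to other implanted mesh, but its code is the stem of the three that follow. In substance these are two codes with their encounter suffixes.

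**Step 2: look for the same codes in the erosion definitions.** The Mesh Erosion row contains 0 of the 8, and so does the erosion and exposure subtype under Re-Operation. An event recorded only as T83.712x or T83.722x therefore counts as perforation and not as erosion. If the same patient also carries one of the broader device-complication codes in the Mesh Erosion row, she is counted there too, so the loss applies to events that carry only the urethral-mesh code.

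**Step 3: look for organ-injury codes.** Bladder and urethral injury (596.6, 867.0/S37) and bowel injury (569.83/S36) occur only among the re-operation subtypes. Follow a bladder injury at the index operation with no later revision or removal:

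- Organ Mesh Perforation: no injury code listed, not counted.
- Mesh Erosion: not counted.
- Re-Operation subtype: needs a re-operation, not counted.
- Urethral Fistula (599.1/N36.0): counted only if that particular sequel develops.

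**Step 4: ask whether free text closes the gap.** The row allows it only as a possibility and gives no search terms or rule. The note extraction described in Section 6 is for surgical approach and for hand-cut or tensioned slings. Perforation is not among its targets.

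**Step 5: test both meanings of the row.**

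- If it means injury at surgery, the codes do not measure it.
- If it means mesh entering an organ, the codes broadly fit. The event is then a form of erosion and still missing from the Mesh Erosion outcome.

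The gap in Mesh Erosion is present under both meanings.

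**The case against.** The strongest reply is that the row is about mesh perforation. Erosion of urethral mesh into surrounding tissue, and exposure into the urethra, are ways for mesh to enter an organ. The note does not say that the event is intra-operative, and the appendix files vaginal-mesh erosion and exposure under a surgical-complications label in two places. This reading is tenable. It means one cannot say that the codes are simply wrong for the row, only that title, note and codes do not settle on one meaning. It does not explain why the same codes are absent from Mesh Erosion.

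A second reply is that injury at the index operation is not a promised endpoint: the aims concern events beyond one and two years, and Section 7 places outcomes in the surveillance period after surgery. This stands, and it limits the weight of the point.

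Two stronger readings should not be drawn.

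- A reader might use the 1.6% of erosions requiring intervention, cited in Section 1.1, to estimate how many erosions would be reported as perforations. The protocol does not support this. The figure comes from an outside registry, and nothing shows what share would carry a urethral-mesh code rather than one of the vaginal-mesh codes.
- A reader might infer that free text would bias the mesh and non-mesh figures, because Section 8.1 collects "free text peri-operative documents for those patient cases that has mesh implantation". No perforation rule for text exists, and under the mesh-entering-organ meaning women without mesh could not have the event. Sections 4 and 9.1 also exclude direct comparison of the groups.

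**Conclusion.** The point holds in a limited form. All 8 entries in the perforation row are labelled erosion or exposure, none of them is in the Mesh Erosion outcome, and the organ-injury codes count only through re-operation. As written, urethral-mesh erosion recorded only under these codes is reported as perforation and is missing from the erosion rate. Organ injury at the index operation without re-operation is counted by no listed injury code.

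The conclusion rests on the appendix labels as printed and on free text having no rule. The perforation row is outside Section 7, so the effect is limited to the reported perforation and erosion rates. All eight entries are ICD-10-CM, so the misplacement arises only in records coded in that system. The number of patients affected cannot be derived from the protocol. The edit is still worth making, because mesh erosion is a named aim and the change is small.

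**What to change.** 1. Add T83.712 and T83.722, with their suffixes, to the Mesh Erosion outcome. This applies whichever meaning is chosen in step 2. It must accompany any removal of these codes from the perforation row; otherwise they would fall under no outcome.
2. Reconcile the perforation row's title, note and codes by stating one meaning.
   - If it is a direct complication of surgery, define it by the bladder and urethral injury codes already listed under Re-Operation. Take them from structured data in both groups, date them from the index operation, and count them whether or not a re-operation follows. Report bowel injury separately, since the row covers vagina and urinary tract. The re-operation list has no code labelled vaginal injury, so that part of the title needs a code or should be dropped. State how this dating fits with Section 7, which places outcomes after surgery.
   - If it is mesh entering an organ, rename it as a subtype of mesh erosion.
3. Either give a rule for the free-text source or delete it.

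The cost is a few lines in the appendix and the matching change in the extraction code. The coded part needs no new data source. The downside of the first option is that structured codes may under-record minor perforations, which should be stated alongside the rate.

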	70.55 Repair of rectocele with graft or prosthesis
	70.53 Repair of cystocele and rectocele with graft or prosthesis
Anterior and Posterior Repair	70.50 Repair of cystocele and rectocele
	70.53 Repair of cystocele and rectocele with graft or prosthesis
Apical Repair	69.2/ 0UN48ZZ, 0UQ40ZZ, 0UQ43ZZ, 0UQ44ZZ, 0UQ48ZZ, 0US48ZZ Repair of
	uterine supporting structures
	70.4/0UTG0ZZ, 0UTG4ZZ, 0UTG7ZZ, 0UTG8ZZ Obliteration and total excision of
	the vagina
	70.77 Vaginal suspension
	70.78/ 0UUG07Z, 0UUG0JZ, 0UUG0KZ, 0UUG47Z, 0UUG4JZ, 0UUG4KZ,
	0UUG77Z, 0UUG7JZ, 0UUG7KZ, 0UUG87Z, 0UUG8JZ, 0UUG8KZ Vaginal
	suspension and fixation with graft or prosthesis
	70.8/ OULG7DZ, OULG7ZZ, OULG8DZ, OULG8ZZ, Obliteration of the vaginal vault
	(LeFort)
	70.92/ 0ULF7DZ, 0ULF7ZZ, 0ULF8DZ, 0ULF8ZZ, 0UQF0ZZ, 0UQF3ZZ, 0UQF4ZZ,
	0UQF7ZZ, 0UQF8ZZ, 0USF0ZZ, 0USF4ZZ, OUSF8ZZ, 0UTF0ZZ, 0UTF4ZZ,
	0UTF7ZZ, 0UTF8ZZ Other operations on cul-de-sac
	70.93/ 0UUF07Z, 0UUF0JZ, 0UUF0KZ, 0UUF47Z, 0UUF4JZ, 0UUF4KZ, 0UUF77Z,
	OUUF7JZ, OUUF7KZ, OUUF87Z, OUUF8JZ, OUUF8KZ Other operations on cul-de-
	sac with graft or prosthesis
	70.95 Insertion of synthetic graft or prosthesis
Hysterectomy	68.3/ OUT90ZL, Subtotal abdominal hysterectomy
	68.39 Other and unspecified subtotal abdominal hysterectomy
	68.4 Total abdominal hysterectomy
	68.49/ 0UT90ZZ, 0UTC0ZZ Other and unspecified total abdominal
	hysterectomy
	68.6/ 0UT44ZZ Radical abdominal hysterectomy

	68.69/ 0UT40ZZ Other and unspecified radical abdominal hysterectomy
	68.5 Vaginal hysterectomy
	68.59/ OUT97ZL Other and unspecified vaginal hysterectomy
	68.7 Radical vaginal hysterectomy
	68.79/ OUT47ZZ, OUT48ZZ, OUT97ZZ, OUT98ZZ, OUTC7ZZ, OUTC8ZZ Other and
	unspecified radical vaginal hysterectomy
	68.31/ OUT94ZL Laparoscopic supracervical hysterectomy
	68.41/ 0UT94ZZ, 0UTC4ZZ Laparoscopic total hysterectomy
	68.51/ OUT9FZL Laparoscopic assisted vaginal hysterectomy
	68.61 Laparoscopic radical abdominal hysterectomy
	68.71/ OUT9FZZ Laparoscopic radical vaginal hysterectomy
	68.9 Other and unspecified hysterectomy
Vaginal Hysterectomy	68.5 Vaginal hysterectomy

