Outcome	Mesh Erosion	Admin Codes: ICD-9-CM codes for mesh erosion: 996.30, 996.39, 996.59, 996.60, 996.65, 996.69, 996.70, 996.76, 996.79, 939.0, 939.2, and 939.9 ICD 10 CM: T83.498A, T85.698A, T85.79XA, T83.598A, T85.79XA, T85.9XXA, T83.89XA, T85.898A, T19.0XXA, T19.2XXA, T19.9XXA Surgical Complications: ICD 9/10 629.31/T83.711 Erosion of implanted vaginal mesh ICD 9/10 629.32/T83.721S Exposure of implanted vaginal mesh ICD 9/10 996.76/T83.9 Complication of genitourinary device, implant or graft ICD9/10-PCS V58.2/30233N1, 30233P1, 30233H1 Blood transfusion ICD9/10 998.5/ T81.49XA, T81.40XS, T81.41, T81.43, T83.5, T83.6 Postoperative infection ICD 9/10 778.2/R33.9 Urinary retention		Capture as date/time Exclude 629.3- complication of implanted vaginal mesh and other prosthetic materials, 629.31- erosion of implanted vaginal mesh, or 629.32-exposure of implanted vaginal mesh because these ICD-9 were not released until 2011? ²⁸ SME determined that topical estrogen could be prescribed for other reasons
Outcome	Urethral fistula	Admin Codes ICD 9- 599.1 ICD 10-N36.0	Yes	Capture as date/time
Covariate	Prior Abdominal Surgery Or Pelvic Radiation	Admin Codes: Personal history of irradiation-V15.3/Z92.3, Irradiation cystitis- N30.4	Yes	Yes/No
	Therapy	CPT/ICD 9/ICD 10 for prior abdominal surgery:		

Protocol 1		[15 July 2020]
	Hysterectomy: 00846, 00855, 00944, 01962,	
	01963, 01969,45126, 51597, 51925, 56308,	
	58150, 58152, 58180, 58200, 58205, 58210,	
	58240, 58260, 58262, 58263, 58265, 58267,	
	58270, 58275, 58280,	
	58285, 58290, 58291, 58292, 58293,	
	58294, 58541, 58542, 58543, 58544,	
	58548, 58550, 58552, 58553, 58554,	
	58570, 58571, 58572, 58573, 58575,	
	58951, 58953, 58954, 59135,	
	59525, 59560, 59561, 59580, 59581	
	/68.9/290.711	
	Cesarean section: 00850, 59500, 59501,	
	59520, 59521, 59540, 59541/649.81/075.82	
	Appendectomy: 44950, 44955, 44960,	
	44970, 49315, 56315/V45.79/Z90.89	
	Hernia repair: 49505, 49507, 49520,	
	49521, 49525, 49550, 49553, 49555,	
	49557, 49560, 49561, 49565, 49566,	
	49570, 49572, 49585, 49587, 49590,	
	49650, 49651, 49652, 49653, 49654,	
	49655, 49656, 49657, 49659/53.5/0WQF0ZZ,	
	0WQF3ZZ, 0WQF4ZZ	
	Cholecystectomy: 47562, 47563, 47564, 47600,	
	47605, 47610, 47612, 47620/51.0-	
	51.04/0FT40ZZ	
	51.04/01 14022	
	Colectomy: 44139, 44140, 44204, 44205, 44206,	
	44141, 44143, 44144, 44145, 44146, 44147,	
	44150, 44151, 44157, 44158, 44160,44320,	
	44322, 44799, 45110, 45111, 45112, 45113,	

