Insertion of mesh or other prosthesis for repair of pelvic floor defect 57267

General Prolapse Repair codes:

Repair of cystocele and rectocele, no graft 70.50 Repair of cystocele, no graft 70.51 Repair of rectocele, no graft 70.52 Other operations on cul-de-sac (repair of vaginal enterocele), no graft 70.92 Vaginal construction, no graft 70.61 Vaginal reconstruction, no graft 70.62 Vaginal suspension and fixation, no graft 70.77 Colpocleisis 70.80 Other uterine suspension 69.22 Vaginal repair of chronic inversion of uterus 69.23 Other repair of uterus and supporting structures 69.29 Other operation on supporting structure of the uterus 69.98 Obliteration of vaginal vault and total excision of vagina 70.4

General Prolapse CPT-4 Codes:

Rectocele repair 45560 Anterior colporrhaphy, repair of cystocele 57240 Posterior colporrhaphy, repair of rectocele 57250 Combined anteroposterior colporrhaphy with enterocele repair 57265 Combined anteroposterior colporrhaphy 57260 Synthetic Mid-Urethral Slings for Stress Urinary Incontinence in Women Protocol 1 Enterocele Repair—vaginal approach 57268 Enterocele Repair — abdominal approach 57270 Colpocleisis 57120 Colpopexy, vaginal, extraperitoneal approach 57282 Colpopexy, vaginal, intraperitoneal approach 57283 Insertion of mesh; vaginal approach 57267 Pereyra procedure, including anterior colporrhaphy 57289 Removal or revision of sling for SUI 57287 Revision (including removal) of prosthetic vaginal graft; vaginal approach 57295 Sling operation for SUI 57288 Uterine suspension 58400 Uterine suspension 58410 Vaginal hysterectomy, with repair of enterocele 58270 Vaginal hysterectomy, with colpourethrocystopexy, complicated 58293 Vaginal hysterectomy with repair of enterocele, complicated 58294

Sling Codes:

Retropubic Urethral Suspension 59.4, 59.71, 59.79 *Must be used concurrently with other prolapse repair codes.

International Classification of Diseases (ICD)-9/10 Diagnosis and Procedure Codes ⁵⁶

Diagnoses

Urinary incontinence	625.6/N39.3 Stress urinary incontinence, female
	599.82/N36.42 Intrinsic sphincter deficiency
	788.30/R32 Urinary incontinence, unspecified
	788.31/N39.41 Urge incontinence
	788.32/N39.3 Stress urinary incontinence, male
	788.33/N39.46Mixed incontinence (male) (female)
	788.34/N39.42 Incontinence without sensory awareness
	788.35/N39.43Post-void dribbling
	788.36/N39.44 Nocturnal enuresis
	788.37/N39.45 Continuous leakage
	788.38/N39.490 Overflow incontinence

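### Within the prior-abdominal-surgery covariate, the ICD procedure codes for hysterectomy are limited to ICD-9 68.9, although the same appendix prints 15 further ICD-9 and 17 ICD-10-PCS hysterectomy codes

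*Protocol*

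**What the plan says.** Section 4 of the protocol names prior abdominal surgery as a covariate, to be present before the index surgery. It is coded in the Data Collection table of Section 13, in the row for prior abdominal surgery or pelvic radiation, as a single Yes/No item. The codes are announced as "CPT/ICD 9/ICD 10 for prior abdominal surgery". The hysterectomy entry begins "Hysterectomy: 00846, 00855, 00944, 01962" and runs to 54 CPT codes. After the slashes come one ICD-9 code, 68.9, and one ICD-10 entry. Further down the row, the scope of the hysterectomy component is given as "abdominal and vaginal".

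The appendix closes with a list headed "International Classification of Diseases (ICD)-9/10 Diagnosis and Procedure Codes", attributed to reference 56. Its hysterectomy rows include "68.5 Vaginal hysterectomy", "68.49/ 0UT90ZZ, 0UTC0ZZ Other and unspecified total abdominal" (hysterectomy), "68.79/ OUT47ZZ, OUT48ZZ, OUT97ZZ, OUT98ZZ, OUTC7ZZ, OUTC8ZZ Other and" (unspecified radical vaginal hysterectomy) and, as the residual category, "68.9 Other and unspecified hysterectomy".

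Section 8.1 lists both CPT and ICD-9/10 procedure codes among the data held across the sites. Section 4 notes that the study spans the ICD-9 and ICD-10 eras.

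**The concern.** The row searches three code systems, but its ICD procedure part for hysterectomy consists of a residual code alone. Abdominal and vaginal hysterectomy, which the row says it covers, have their own ICD-9 and ICD-10-PCS codes a few pages later, and the row uses none of them. No reason is given.

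If a woman's hysterectomy is on file only under one of those codes, she joins the group with no prior surgery. If such misses are unrelated to outcome, they dilute the covariate as a candidate predictor in the site-level LASSO Cox models of Section 9.1. What is at stake is the accuracy of one descriptive count and one predictor. Mesh and non-mesh groups are not compared directly, so no treatment contrast depends on it.

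**Working it through.** No sample-size or error-rate figure is involved. The check compares two printed code sets. The letter O at the start of some ICD-10-PCS codes is read as zero.

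**Covariate row, hysterectomy entry (Section 13, Data Collection table)**
- CPT: 54 distinct codes, from 00846 to 59581.
- ICD-9 procedure: 68.9 only, 1 code.
- ICD-10-PCS: 0 codes. The single ICD-10 entry is printed as 290.711. That is not in procedure-code form and may be a text-reading fault, so nothing here rests on it.

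**Closing list, hysterectomy rows (Section 13)**
- ICD-9: 68.3, 68.31, 68.39, 68.4, 68.41, 68.49, 68.5, 68.51, 68.59, 68.6, 68.61, 68.69, 68.7, 68.71, 68.79, 68.9 = 16 distinct codes. The separate vaginal hysterectomy row repeats five of these and adds none.
- ICD-10-PCS, counted by the ICD-9 code they accompany: 68.3 (1), 68.31 (1), 68.41 (2), 68.49 (2), 68.51 (1), 68.59 (1), 68.6 (1), 68.69 (1), 68.71 (1), 68.79 (6). Sum: 1 + 1 + 2 + 2 + 1 + 1 + 1 + 1 + 1 + 6 = 17 distinct codes.

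**Difference**
- ICD-9 codes absent from the covariate: 16 − 1 = 15.
- ICD-10-PCS codes absent: 17 − 0 = 17.

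Five of the 15 absent ICD-9 entries (68.3, 68.4, 68.5, 68.6, 68.7) are headings whose subdivisions are also listed, so 15 counts list entries, not separate operations.

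**Were ICD procedure codes meant to count?** Yes. Other operations in the same row use specific ones: colectomy has 45.8, 45.81, 45.82 and 45.83 plus four ICD-10-PCS codes; lysis of adhesions has 54.5, 54.51 and 54.59 plus a run of ICD-10-PCS codes; hernia repair has 53.5 plus three. The hysterectomy entry's own ICD-9 code, 68.9, is also a procedure code.

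**Who is missed?** A woman with a prior hysterectomy is scored No only if all of these hold:
1. none of the 54 CPT codes is on file;
2. neither 68.9 nor the row's ICD-10 entry is on file;
3. the hysterectomy is recorded by one of the 15 + 17 omitted codes;
4. no other operation or radiation code in the row is on file.

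The protocol gives no frequency for any of these conditions, so the proportion cannot be computed.

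**The case against.** The strongest reply is that the CPT list does most of the work. It includes specific operations: 58270, 58293 and 58294, which the appendix itself describes as particular vaginal hysterectomies, are all in the row. A reader might infer from the lone 68.9 that hysterectomies with a specific procedure code are generally scored as no prior surgery. The protocol does not support that, because CPT codes are procedure codes and any listed one gives a Yes. This part of the reply stands and limits the point to records held only in ICD procedure codes.

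Secondly, the closing list is taken from a cited source and is not labelled as the covariate's definition. That is also true, so the mismatch is a gap in completeness and not a contradiction between two definitions. It does not explain why the row searches ICD procedure codes yet stops at the residual one.

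Three further inferences are tempting and should not be drawn:
- **Worse error at some sites.** Section 8.1 lists the same code systems across all sites, and no passage describes a site that holds surgical history mainly as ICD procedure codes.
- **A figure for the attenuated hazard ratio.** The prevalence of prior surgery, its true effect and the share captured are all absent from the protocol.
- **The same gap for cystocele and rectocele repair.** That entry shows 70.50 as its only ICD-9 code, but it also has CPT 57240 and the ICD-10-PCS codes 0JQC0ZZ and 0JQC3ZZ, which the closing list pairs with both 70.51 and 70.52.

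**Conclusion.** The point holds in a limited form. The ICD procedure part of the hysterectomy definition contains 1 of the 16 ICD-9 codes and 0 of the 17 ICD-10-PCS codes printed in the same appendix, and it falls short of the row's stated scope. Hysterectomies with a listed CPT record are captured. Those recorded solely by an omitted ICD procedure code, in women with no other qualifying code, are not.

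The number of such women is unknown and could be negligible. The conclusion assumes that the covariate is extracted as the row is written, and that some records carry an ICD procedure code without a listed CPT code; the protocol neither confirms nor excludes the latter. This is a minor correction, worth making because it costs almost nothing.

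**What to change.** In the hysterectomy entry of the prior-abdominal-surgery row, add the 15 missing ICD-9 codes and the 17 ICD-10-PCS codes from the closing list. Keep the 54 CPT codes, 68.9 and the existing ICD-10 entry. The entry would then hold 54 CPT, 16 ICD-9 and 17 ICD-10-PCS codes besides that entry. When copying, check that each ICD-10-PCS code begins with a zero and not the letter O. No new timing rule is needed, since Sections 4 and 6 already restrict covariates to those present before surgery.

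The cost is an edit to one code list and to the extraction code. The sites already hold the fields. Counting the women who change from No to Yes after the edit would show how much the gap mattered.
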